8.2.5 Medical History and Demographic Data

Medical history includes clinically significant diseases, surgeries, cancer history (including prior cancer therapies and procedures), reproductive status, smoking history, use of alcohol and drugs of abuse, and all medications (e.g., prescription drugs, OTC drugs, herbal or homeopathic remedies, nutritional supplements) used by the participant within 30 days prior to the screening visit.

Demographic data will include age, sex, and self-reported race/ethnicity.

8.2.6 SARS-CoV-2 Tests (If Required)

Testing for the SARS-CoV-2 virus may be performed based on current infection rates and availability of tests. Tests will be performed according to the time schedule presented in Section 1.3. The samples will be collected and processed as detailed in the Screening Sample Processing Manual and Clinical Sample Processing Manual.

Testing time points may be changed and additional time points may be added throughout the study as required. The decision on COVID-19 testing and the definition of the testing time points will be agreed by the study team and documented in the ISF via the Clinical Kick-Off Meeting minutes.

8.3 ADVERSE EVENTS AND SERIOUS ADVERSE EVENTS

The definitions of an AE or SAE can be found in [Appendix 2](#). The NSAESI are discussed in Sections [8.3.6](#).

The Investigator and any qualified designees are responsible for ensuring that all AEs (including assessment of seriousness, severity, and causality; see [Appendix 2](#)) are recorded on the AE eCRF and reported to the Sponsor in accordance with instructions provided in this section and in [Appendix 2](#).

Procedures used for recording AEs are provided in [Appendix 3](#):

- Diagnosis versus signs and symptoms:
 - Infusion reactions
 - Other AEs
- AEs occurring secondary to other events
- Persistent or recurrent AEs
- Abnormal laboratory values

- Abnormal vital sign values
- Abnormal liver function tests
- Deaths
- Preexisting medical conditions
- Hospitalization or prolonged hospitalization

8.3.1 Time Period and Frequency for Collecting Adverse Event and Serious Adverse Event Information

The method of recording, evaluating, and assessing causality of AEs and SAEs and the procedures for completing and transmitting SAE reports are provided in [Appendix 2](#).

Investigators will seek information on AEs at each participant's contact. All AEs, whether reported by the participant or noted by study personnel, will be recorded in the participant's medical record and on the AE eCRF as follows:

After informed consent has been obtained **but prior to initiation of study treatment**, only SAEs caused by a protocol-mandated intervention should be reported (e.g., SAEs related to invasive procedures such as biopsies). Any other AE should not be reported.

After initiation of study treatment, all AEs, regardless of relationship to study treatment, will be reported until 28 days after the last dose of study treatment.

Post-study AEs and SAEs: The Investigator is not required to actively monitor participants for AEs after the end of the AE reporting period (28 days after the last dose of study treatment).

However, if the Investigator learns of any SAE (including a death) or other AEs of concern that are believed to be related to prior treatment with study treatment, at any time after a participant has been discharged from the study, and the Investigator considers the event to be reasonably related to the study treatment or study participation, the Investigator must promptly notify the Sponsor. For the procedure of reporting, see [Appendix 2](#).

8.3.2 Method of Detecting Adverse Events and Serious Adverse Events

Care will be taken not to introduce bias when detecting AEs and/or SAEs. Open-ended and non-leading verbal questioning of the participant is the preferred method to inquire about AE occurrence.

A consistent methodology of non-directive questioning should be adopted for eliciting AE information at all participant evaluation time points.

8.3.3 Follow-Up of Adverse Events and Serious Adverse Events

8.3.3.1 Investigator Follow-Up

The Investigator should follow-up each AE until the event has resolved to baseline grade or better, the event is assessed as stable by the Investigator, the event is otherwise explained, the participant is lost to follow-up (Section 7.3), or the participant withdraws consent. Every effort should be made to follow all SAEs considered to be related to study treatment or study-related procedures until a final outcome can be reported.

During the study period, resolution of AEs (with dates) should be documented on the AE eCRF and in the participant's medical record to facilitate source data verification. If, after follow-up, return to baseline status or stabilization cannot be established, an explanation should be recorded on the AE eCRF.

All pregnancies reported during the study should be followed until pregnancy outcome and reported according to the instructions provided in Section 8.3.5.

8.3.3.2 Sponsor Follow-Up

For SAEs, NSAESIs, and pregnancies, the Sponsor or a designee may follow-up by telephone, fax, electronic mail, and/or a monitoring visit to obtain additional event details and outcome information (e.g., from hospital discharge summaries, consultant reports, autopsy reports) in order to perform an independent medical assessment of the reported event.

8.3.4 Regulatory Reporting Requirements for Serious Adverse Events

Prompt notification by the Investigator to the Sponsor of a SAE is essential so that legal obligations and ethical responsibilities towards the safety of participants and the safety of a study treatment under clinical investigation are met.

The Sponsor has a legal responsibility to notify both the local regulatory authority and other regulatory agencies about the safety of a study treatment under clinical investigation. The Sponsor will comply with country-specific regulatory requirements relating to safety reporting to the regulatory authority, IRB/IEC, and Investigators.

Investigator safety reports must be prepared for suspected unexpected serious adverse reactions according to local regulatory requirements and Sponsor policy and forwarded to Investigators as necessary.

An Investigator who receives an Investigator safety report describing a SAE or other specific safety information (e.g., summary or listing of SAEs) from the Sponsor will review and then, file it along with the IB and will notify the IRB/IEC, if appropriate according to local requirements.

For immediate and expedited reporting requirements from Investigator to Sponsor and from Sponsor to Health Authority, Investigators, IRB and EC, see [Appendix 2](#).

8.3.4.1 Emergency Medical Contacts

To ensure the safety of study participants, access to the Medical Monitors is available 24 hours a day, 7 days a week. Medical monitors contact details will be available on a separate list generated by the study management team.

8.3.5 Pregnancy

Female participants of childbearing potential will be instructed to immediately inform the Investigator if they become pregnant during the study or within 90 days after the final dose of study treatment.

Male participants will be instructed through the ICF to immediately inform the Investigator if their partner becomes pregnant during the study or within 90 days after the final dose of study treatment.

If a pregnancy is reported, the Investigator should inform the Sponsor within 24 hours of learning of the pregnancy and should follow the pregnancy reporting process as detailed in [Appendix 5](#).

Abnormal pregnancy outcomes (e.g., spontaneous abortion, fetal death, stillbirth, congenital anomalies, ectopic pregnancy) are considered SAEs ([Appendix 5](#)).

8.3.6 Non-Serious Adverse Events of Special Interest

NSAESI are required to be reported by the Investigator to the Sponsor immediately (i.e., no more than 24 hours after learning of the event; see [Appendix 2](#) for reporting instructions).

NSAESI for this study include the following:

- Cases of an elevated ALT or AST in combination with either an elevated bilirubin or clinical jaundice, as defined in [Appendix 3](#).
- Suspected transmission of an infectious agent by the study treatment, as defined below:
 - Any organism, virus, or infectious particle (e.g., prion protein transmitting transmissible spongiform encephalopathy), pathogenic or non-pathogenic, is considered an infectious agent. A transmission of an infectious agent may be suspected from clinical symptoms or laboratory findings that indicate an

infection in a participant exposed to a medicinal product. This term applies only when a contamination of the study treatment is suspected.

8.4 TREATMENT OF OVERDOSE

Study treatment overdose is the accidental administration of a drug in a quantity that is higher than the assigned dose. An overdose or incorrect administration of study treatment is not an AE unless it results in untoward medical effects (see Sections 5 and 5.2 of [Appendix 2](#) for further details).

Decisions regarding dose-interruptions or modifications (if applicable) will be made by the Investigator in consultation with the Medical Monitor based on the clinical evaluation of the participant.

In the event of an overdose, the Investigator should:

1. Contact the Sponsor's Medical Monitor immediately.
2. Closely monitor the participant for AE/SAE and laboratory abnormalities until resolved.
3. Obtain a blood sample for PK analysis within 24 hours from the date of the final dose of study treatment, if requested by the Medical Monitor (determined on a case-by-case basis).
4. Document the quantity of the excess dose, as well as the duration of the overdose, in the CRF.

For this study, any dose of RO7049389 greater than 1600 mg within a 24-hour time period (+ 1.0 hour) will be considered an overdose.

The Sponsor does not recommend specific treatment for an overdose.

8.5 PHARMACOKINETICS

Mandatory blood and urine samples to evaluate concentrations of study treatment (RO7049389) and its metabolites (RO7121986, RO7255420, and/or RO7255422) will be collected. Mandatory blood, urine, and feces samples to measure the radioactivity and metabolic profiling will be also collected. The date and time of each sample collection will be recorded in the eCRF. The PK samples will be taken as outlined in the SoAs (Section [1.3](#)).

A PK sample will also be collected following occurrence of a dose-limiting event or SAE.

- Total radioactivity will be measured in plasma, whole blood, urine, and feces samples from MB cohort by liquid scintillation counting (LSC, Pharmaron, Hoddesdon EN11 9FH UK). Samples with low levels of radioactivity that cannot be quantified by LSC may be analyzed using AMS, if necessary.

- Metabolic profiling will be conducted in plasma, urine, and feces and blood pellet (if appropriate). The metabolic profiling samples may not be assessed if there are insignificant levels of [¹⁴C]-radioactivity present. The best approach for the pooling strategy of metabolic profiling samples (e.g., urine, feces, plasma, and blood pellet) must be agreed upon between the clinical study site and the Sponsor prior to being performed. The results of the metabolic profiling analysis may be reported separately from the main clinical study report.
- Concentrations of [¹²C] RO7049389, [¹²C] RO7121986, [¹²C] RO7255420 and [¹²C]-RO7255422 in plasma samples from both MB cohort and absolute BA cohort will be measured using a validated liquid chromatography–mass spectrometry (LC-MS/MS) method by Q2 solution (Ithaca, NY 14850 USA).
- Concentrations of [¹³C] RO7049389 and [¹³C] RO7121986 in plasma samples from both MB cohort and absolute BA cohort will be measured using a validated LC-MS/MS method by Q2 solution (Ithaca, NY 14850 USA).
- Concentrations of [¹²C] RO7049389, [¹²C] RO7121986, [¹²C] RO7255420 and [¹²C] RO7255422 in urine samples from absolute BA cohort will be measured using a validated LC-MS/MS method by Q2 solution (Ithaca, NY 14850 USA).
- Concentrations of RO7049389 other new identified metabolite(s) from absolute BA cohort as appropriate in plasma and urine samples may be measured using a validated LC-MS/MS method by Q2 solution (Ithaca, NY 14850 USA).

If required, remaining PK samples may also be used for assay development/validation experiments.

The PK blood samples will be destroyed 2 years after the date of final clinical study report (CSR), unless regulatory authorities require specimens to be maintained for a longer period. Details on sampling procedures, sample storage, and shipment are given in the Sample Handling Manual.

The acceptable deviations from the nominal blood sampling times are as follows:

- The pre-dose samples will be taken \leq 1 hour before dosing
- 0 to 1 hour post-dose samples will be taken within \pm 2 minutes of the nominal post-dose sampling time
- 1.5 to 12 hours post-dose samples will be taken within \pm 10 minutes of the nominal post-dose sampling time
- 24 hours to 264 hours post-dose samples will be taken within \pm 30 minutes of the nominal post-dose sampling time.

8.6 PHARMACODYNAMICS AND BIOMARKERS ANALYSES

PD parameters are not evaluated in this study.

8.6.1 Clinical Genotyping

The DNA will be used for, but analysis is not limited to:

- [REDACTED]

Data arising from all biosamples including samples for analyses of inherited DNA will be subject to confidentiality standards described in [Appendix 1](#).

8.7 PHARMACODYNAMICS AND BIOMARKER SAMPLES

No PD samples would be collected in this study.

A mandatory whole blood sample will be taken for DNA extraction from every participant. If the sample is missed on Day 1, it can be collected at any other scheduled visit.

The samples will be destroyed within 5 years after the date of final CSR, unless regulatory authorities require specimens to be maintained for a longer time period. Details on sampling procedures, sample storage, and shipment are given in the Sample Handling Manual.

8.8 HEALTH ECONOMICS

Health Economics/Medical Resource Utilization and Health Economics parameters are not evaluated in this study.

8.9 TIMING OF STUDY ASSESSMENTS

8.9.1 Screening and Pre-treatment Assessments

Written informed consent for participation in the study must be obtained before performing any study-specific screening tests or evaluations. ICFs for enrolled participant and for participants who are not subsequently enrolled will be maintained at the study site.

All screening and pre-treatment assessments (related to entry criteria), must be completed and reviewed to confirm that participants meet all eligibility criteria. The Investigator will maintain a screening log to record details of all participants screened and to confirm eligibility or record reasons for screening failure.

An Eligibility Screening Form documenting the Investigator's assessment of each screened participant with regard to the protocol's inclusion and exclusion criteria is to be completed by the Investigator and kept at the investigational site.

Screening and pre-treatment assessments will be performed within 28 days prior to Day 1, unless otherwise specified.

8.9.2 Assessments during Treatment

Under no circumstances, will participants who enroll in this study and have completed treatment as specified, be permitted to re-enroll in the study.

All assessments must be performed as per the SoAs (Section 1.3). Assessments scheduled on the day of study treatment administration should be performed prior to administration of study treatment, unless otherwise noted in the SoAs.

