During the Period 1 of the absolute bioavailability (BA) cohort, infusion pain events occurred in several participants after administration of [¹³C]-labeled RO7049389. These adverse events (AEs) were identified to be most likely related to high concentration of potassium in the infusion solution of [¹³C]-labeled RO7049389. Although these AEs were transient and the participants recovered soon after the infusion, Study BP41811 was temporarily halted after the completion of Period 1. The Sponsor amended this study protocol to ensure participant's safety. Changes to the protocol, along with a rationale for each change, are summarized below:

- In Table 3 (Section 1.3), the missing footnote (h) "Follicle stimulating hormone (females only to confirm post-menopausal status, performed at screening only)" has been added.
- Following Medicines and Healthcare products Regulatory Agency (MHRA) guidance relating to the management of COVID-19 vaccine deployment for ongoing non-COVID-19 clinical trials, Section 2.3.1.3 (Assessment Regarding COVID-19 Vaccination) has been added.
- Section 4.1 and Section 4.1.2 have been updated to remove the upper limit of the washout period (21 days) and to allow participants to be discharged after completing Period 1 and re-admitted for Period 2. The longer washout period is not considered to affect either the safety of participants or the integrity of the study. As the study is temporarily halted, the 21-day washout period will not be sufficient for the administration process; this amendment is to provide flexibility to keep the participants who have completed Period 1 to continue with Period 2.
- Since the upper limit of the washout period is removed and the participants are allowed to discharge from the site between the two periods of the absolute BA cohort, requirement for re-assessment of exclusion criteria 7, 8, 15 and 16 before admission/pre-dose of each treatment period have been added (Section 5.2).
- Section 5 and Section 9.1 have been update to remove the sentence "Up to 4 participants of each ethnic group can be replaced." As the participants have been discharged from the site and the washout period will be longer than 21 days, participants who prematurely discontinued from the study may be replaced due to non-safety related issues.

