- d) Samples for clinical laboratory tests (hematology, chemistry, coagulation, urinalysis, and lipids) should be collected in the morning/at the most appropriate time. Creatinine clearance (CrCl) will be calculated using the Cockcroft-Gault formula at screening *and on Day -1*.
- e) Hepatitis A virus (HAV) IgM antibody, hepatitis B surface antigen (HBsAg), hepatitis C virus (HCV) RNA, total hepatitis D virus (HDV) antibody, hepatitis E virus (HEV) IgM antibody, human immunodeficiency virus (HIV-1 antibody and HIV-2 antibody, or HIV-1/2 antibody).
- f) Testing for SARS-CoV-2 may be performed based on current infection rates and availability of tests. If required, SARS-CoV-2 antibody will be done at screening. SARS-CoV-2 antigen will be done at screening, pre-admission, day before discharge *or* day of discharge.
- g) Radioactivity counting will be continued until discharge criteria are met.
- h) If the blood sample is not collected on Day 1, it may be collected at any time during the conduct of the clinical study.
- i) The participant will not be discharged until criteria are met. This is up to a maximum of 264 hours post-dose (Day 12) in-clinic stay, and could include a further 5 days collection of urine and feces samples at home, if required.
- j) Assessments done on the day of discharge. Tests should be performed after an overnight fast (for at least 10 hours).
- k) Only one sample is collected. It will be kept and processed only if the pre-dose sample on Day 1 cannot be obtained.
- l) Only collecting the PK sample.

Table 2 Mass Balance Cohort – Detailed Table

Period	Day	Scheduled Time (h)	Oral Administration of [¹⁴ C] RO7049389 suspension	IV Administration of [¹³ C] RO7049389 solution	Blood sampling for PK of [¹³ C] RO7049389 and its [¹² C] metabolites	Blood sampling for PK of [¹³ C] RO7049389 and [¹³ C] M5	Blood sampling for [¹⁴ C] drug related material radioactivity counting	Blood sampling for [¹⁴ C] drug related material metabolic profiling	Urine sampling for [¹⁴ C] drug related material radioactivity counting and metabolic profiling	Feces sampling for [¹⁴ C] drug related material radioactivity counting and metabolic profiling
Screening	Day -28 to Day -2									
	Day -1									^f
Period 1	Day 1	Pre-dose			X		X	X	X ^e	X
		0	X ^a							
		0.5			X		X			
		1			X		X	X		
		1.5			X		X			
		2	X ^b	X ^c	X ^c		X ^c	X ^c		
		2.1333			X ^d					
		3			X	X	X			
		4			X	X	X	X		
		6			X	X	X			
		8			X	X	X	X		
		10			X	X	X			
		12			X	X	X	X		

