	Day 2	24			X	X	X	X	12-24 hr	
		36			X	X	X	X		24-48 hr
	Day 3	48			X	X	X	X		24-48 hr
	Day 4	72			X	X	X	X	48-72 hr	48-72 hr
	Day 5	96					X	X	72-96 hr	72-96 hr
	Day 6	120					X	X ^g	96-120 hr	96-120 hr
	Day 7	144					X	X ^g	120-144 hr	120-144 hr
	Day 8	168					X		144-168 hr	144-168 hr
	Day 9	192					X ^h		168-192 hr ^h	168-192 hr ^h
	Day 10	216					X ^h		192-216 hr ^h	192-216 hr ^h
	Day 11	240					X ^h		216-240 hr ^h	216-240 hr ^h
	Day 12	264					X ^h		240-264 hr ^{h,i}	240-264 hr ^{h,i}

Table 2 Mass Balance Cohort – Detailed Table (cont.)

- a) Participants will fast overnight for at least 10 hours prior to oral administration and fasted 4 hours post administration.
- b) Intravenous infusion administration over 10 minutes.
- c) Collected prior to start of infusion.
- d) Collected at the end of infusion.
- e) Spot urine sample.
- f) Only one sample is collected. It will be kept and processed only if the pre-dose sample on Day 1 cannot be obtained.
- g) Metabolic profiling analyses may not be done depending on the radioactivity level.
- h) Continued until discharge criteria are met.
- i) If on Day 12 the discharge criteria are not met, the participant will be discharged and, urine and feces samples will be collected by the subject at home in 24 hours intervals for up to 5 days or until the discharge criteria are met.

Table 3 Absolute BA Cohort – Main Table

Assessments	Screening		Treatment Period				Follow Up Call Period 2, Day 29±3	Early termination or Unscheduled visit
	Day -28 to Day -2	Day -1	Day 1	Day 2	Day 3	Day 4		
Time Relative (h)			0	24	48	72		
Assessments								
Informed Consent	X							
Eligibility	X	X						
Demography	X							
Medical History	X	X						
Vein assessment for venipunctures/cannulation	X							
Physical Examination ^a	X	X				X		X
Vital Signs ^b	X	X	X			X		X
ECG-12 lead ^c	X	X	X			X		X
Hematology ^d	X	X				X		X
Blood Chemistry ^d	X	X				X		X
Coagulation ^d	X	X				X		X
Urinalysis ^d	X	X				X		X
Viral Serology ^e	X							
SARS-CoV-2 ^f	X	X				X		X
Lipids ^d	X	X				X		X
Drug/Alcohol Test	X	X						
Pregnancy Test ^g	X	X						X
Follicle Stimulating Hormone ^h	X							
Oral Administration of [¹² C] RO7049389 tablet			X					
IV Administration of [¹³ C] RO7049389 solution			X					
Blood sampling for PK			X	X	X	X		X
Urine sampling for PK			X	X	X	X		
Clinical Genotyping ⁱ			X					
In-Clinic Stay		X	X	X	X			
Discharge ^j						X		
Adverse Events					X			
Previous and Concomitant Treatments					X			

RO7049389 —F. Hoffmann-La Roche Ltd

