3. OBJECTIVES AND ENDPOINTS

	Objectives	Endpoints
Primary	
 To characterize the mass balance (MB), routes, and rates of elimination of [¹⁴C] RO7049389. To determine the absolute oral bioavailability (BA) of RO7049389. 	
 Percentage of dose excreted in urine. Percentage of dose excreted in feces. Absolute oral BA for RO7049389.
Secondary		
 •
	
 To determine the plasma concentration of RO7049389, its identified three metabolites (RO7121986, RO7255420, and RO7255422), total drug-related radioactivity and related pharmacokinetic (PK) parameters. 	
 C_{max}, AUC_{last}, AUC_{0-inf}, t_{max}, CL/F, CL, CL_r, Ae, V/F, and $t_{1/2}$ of RO7049389 and its identified three metabolites, and total drug-related radioactivity, if appropriate.
	
 To identify and quantify circulating and excreted metabolites of RO7049389 in plasma, urine, and fecal samples based on radioactive metabolic profiling. 	
 A metabolic profile for RO7049389 and metabolites, and their structural elucidation, if appropriate. C_{max}, AUC_{last}, AUC_{0-inf}, t_{max}, CL/F, CL_r, Ae, V/F and $t_{1/2}$ of other major metabolites related radioactivity, if appropriate.
	
 To evaluate the safety and tolerability of one or two single-doses of RO7049389 in healthy participants. 	
 Adverse events (AEs), clinical laboratory values, vital signs, electrocardiogram (ECG), and physical examination.

OBJECTIVES AND ENDPOINT (CONT.)

Exploratory		
	
• To determine whether genes relating to drug-metabolizing enzymes and/or drug transporters affect the PK and/or the safety profile of RO7049389.	
• The pharmacogenetics of metabolizing enzymes (CYP3A4, UGT1A3) and transporters (OATP1B) possibly involved in the absorption, distribution, metabolism, and excretion of RO7049389 and its major metabolites.
	
• To determine the relative BA of RO7121986.	
• C_{max}, AUC_{last}, $AUC_{0-\infty}$ of RO7121986 after oral and intravenous (IV) administration of RO7049389.

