4.1.2 Length of the Study

The identity of the participants will be confirmed at admission and pre-dose. In addition, the ongoing eligibility of participants will be re-assessed at admission/pre dose, as described in Section 5.1 and Section 5.2. Admission/pre-dose safety procedures such as safety bloods tests, ECGs, vital signs, urinalysis, and drugs of abuse tests can be repeated as clinically indicated under the discretion of Investigator or sub-investigator if there is a concern regarding a participant's safety or eligibility to participate in the clinical trial. Reserve participants for the first dose occasion, in any group, will not require admission procedures to be repeated if dosing is within 2 days.

The participants will be admitted to the clinical unit on the morning before dosing (Day -1).

In addition, participants may be required to visit the clinical unit on the day before admission for each treatment period for SARS-CoV-2 antigen tests (if required).

In the MB cohort, the total duration of the study for each participant will be about 8 weeks, divided as follows:

- Screening: Up to 28 days.
- In-clinic period: Day -1 to the day when the discharge criteria (See Section 4.1.1) are met. This is up to a maximum of 12 days.
- Safety follow-up: One call on Day 29 ± 3.

In the absolute BA cohort, the total duration of the study for each participant will be *at least 9 weeks*, depending on the duration of the washout period, divided as follows:

- Screening: Up to 28 days.
- In-clinic period: Days -1 to 4 for both Periods 1 and 2.
- Washout period: Defined as from Period 1 Day 1 to Period 2 Day 1 and lasts at least 7 days.
- Safety follow-up: One call on Period 2 Day 29 ± 3.

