11. Are currently enrolled in or have participated in any other clinical study involving an investigational product or in any other type of medical research within the last 90 days (or within 5 half-lives of the investigational product, whichever is longer).
12. Donation or loss of blood or blood products in excess of 500 mL within three months of screening.

Diagnostic Assessments

13. Clinically relevant ECG abnormalities on screening, Day -1, or Day 1 (pre-dose), e.g.:

- a. QT corrected for heart rate (HR) using the Fridericia's correction factor (QTcF) > 430 msec (males), > 450 msec (females), or < 300 msec (males and females).
- b. Notable resting bradycardia (HR < 45 beats per minute [bpm]), or HR > 90 bpm.
- c. Evidence of atrial fibrillation, atrial flutter, complete bundle branch block, Wolf-Parkinson-White Syndrome, or cardiac pacemaker.

14. Clinically significant ECG with QRS complex (QRS) and/or T-wave judged by the Investigator to be unfavorable for a consistently accurate QT measurement (e.g., neuromuscular artifact that cannot be readily eliminated, arrhythmias, indistinct QRS onset, low amplitude T-wave, merged T- and U-waves, prominent U-waves).

15. Creatinine clearance (CrCl) \leq 70 mL/min (using the Cockcroft-Gault formula) at screening (may be repeated for confirmation) *or on Day -1*.

16. Evidence of current severe acute respiratory syndrome coronavirus 2 (SARS-CoV-2; i.e., the virus that causes COVID-19) infection.

17. Positive test at screening of any of the following: hepatitis A virus (HAV immunoglobulin M [IgM] antibody), hepatitis B virus (HBV, HBsAg), hepatitis C virus (HCV ribonucleic acid [RNA]), hepatitis D virus (total HDV antibody), hepatitis E virus (HEV IgM antibody), and human immunodeficiency virus (HIV-1 antibody and HIV-2 antibody, or HIV-1/2 antibody).

18. Any other clinically significant abnormalities in laboratory test results at screening or on Day -1. In the case of uncertain or questionable results, tests performed during screening or Day -1 may be repeated once prior to enrollment to confirm eligibility unless deemed not clinically significant by the Investigator.

Other Exclusions

- 19. History of any drug or alcohol abuse in the past 2 years.
- 20. Regular alcohol consumption in males > 21 units per week and in females >14 units per week (1 unit = $\frac{1}{2}$ pint beer, or a 25 mL shot of 40% spirit, 1.5 to 2 units = 125 mL glass of wine, depending on type).

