6.1 TREATMENTS ADMINISTERED

[Table 5](#) summarizes the treatments administered. Guidelines for dosage modification and treatment interruption or discontinuation are provided in [Section 6.6](#) or [Section 7](#), respectively.

6.1.1 [¹⁴C] RO7049389 Oral Suspension, 600 mg (NMT 2.2 MBq)

On the morning of Day 1 for MB cohort, a 20-mL drinking suspension containing 600 mg of RO7049389, providing a maximum of 2.2 MBq of [¹⁴C]-labeled RO7049389 (equivalent to 59.3 µCi) will be administered to all eligible participants after an overnight fast of at least 10 hours, followed by another four hours of fasting until lunch. Each participant will receive 190 mL of still water immediately after the dose has been swallowed, followed by a further 50 mL which will be used to rinse out the dosing vessels (50 mL will be used in five separate rinses). Water will be allowed ad libitum until 1 hour prior to dosing and from 1-hour post dosing, at a maximum of three liters a day.

6.1.2 [¹³C] RO7049389 Solution for Infusion, 20 µg/mL

On Day 1 of MB cohort, on Day 1 of both Period 1 and Period 2 of absolute BA cohort, a single microdose of [¹³C]-labeled RO7049389 100 µg will be administered by a 10-minute constant IV infusion. *Dilution of the [¹³C]-labeled RO7049389 solution for infusion using 0.9% saline will be performed at bedside.* The IV infusion will start 2 hours after administration of the oral dose of RO7049389.

Details on study drug preparation by the Quotient Sciences clinical unit will be described in the manufacturing batch record, which will be prepared by the Quotient Sciences pharmacy.

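### No vital sign, ECG or dedicated infusion-site check is scheduled between Day 1 pre-dose and Day 4 (BA cohort) or discharge (MB cohort), so the post-dose windows have no Day 1 time point

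*Combined protocol and SAP*

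**What the plan says.** **Schedule.** In Section 1.3, "Table 3 Absolute BA Cohort – Main Table" marks vital signs and ECG at screening, Day -1, Day 1 (the 0 h column) and Day 4 (72 h); Days 2 and 3 are blank. Table 1 (MB cohort) has the same marks up to Day 1. Its next mark carries footnote j: "Assessments done on the day of discharge". Tables 2 and 4, which give clock times, list only dosing and the pharmacokinetic (PK), radioactivity, profiling and excreta samples. No table has an infusion-site row.

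**Timing rule.** Section 8.9.2 states: "Assessments scheduled on the day of study treatment administration should be performed prior to administration of study treatment, unless otherwise noted in the SoAs". Two other places agree that the Day 1 set is pre-dose. Exclusion criterion 13 covers "Clinically relevant ECG abnormalities on screening, Day -1, or Day 1 (pre-dose", and Section 4.1.2 refers to "Admission/pre-dose safety procedures such as safety bloods tests, ECGs, vital signs, urinalysis". Sections 8.2.2 and 8.2.3 nevertheless set ±15-minute windows for post-dose vital signs and ECG, apart from the pre-dose, discharge and return-visit windows.

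**Endpoints.** Section 3 lists, for the secondary safety objective, "Adverse events (AEs), clinical laboratory values, vital signs, electrocardiogram (ECG), and physical examination".

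**Amendment.** The Version 3 rationale reports that in BA Period 1 "infusion pain events occurred in several participants after administration of [¹³C]-labeled RO7049389", and that the study was halted after that period. Section 6.1.2 now says that dilution of the labelled "solution for infusion using 0.9% saline will be performed at bedside". Dose and infusion time are unchanged. The listed changes add no observation after the infusion.

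**The concern.** The infusion has been changed because of a local tolerability problem, and BA participants who continue to Period 2 will receive the changed form together with a higher oral dose (1000 mg after 600 mg). Potassium is named only as the most likely cause. Yet the schedule asks for no timed, uniform observation after the infusion.

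Two things are at stake. First, vital signs and ECG are listed safety endpoints. In each BA period their only scheduled post-dose value is at 72 h, far from both the infusion and the estimated oral t_max of 2 h. Summaries built on that schedule cannot describe what happens near peak exposure. Second, a visible sign at the infusion site that the participant does not mention has no scheduled check.

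The ±15-minute windows also leave the site unsure whether a post-dose set was intended and lost its time point, or was never intended.

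**Working it through.** The documents state no figure for this gap, so there is nothing of the plan's own to reproduce. The check is clock arithmetic.

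**Inputs.** Infusion start 2 h after the oral dose, lasting 10 min (Section 6.1.2); BA Day 4 = 72 h (Table 3); earliest MB discharge, the morning of Day 8 = 168 h (Section 4.1.1, Table 2); latest MB discharge from the unit, Day 12 = 264 h (Table 1, footnote i); estimated oral t_max 2 h (Section 4.2); discharge window ±1 h (Sections 8.2.2 and 8.2.3).

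**Gap to the next scheduled vital signs and ECG.** Infusion end = 2 + 10/60 = 2.17 h.
- BA: 72 − 2.17 = 69.8 h after infusion end. With the ±1 h window it is 68.8 to 70.8 h.
- BA from oral t_max: 72 − 2 = 70.0 h.
- MB, Day 8: 168 − 2.17 = 165.8 h.
- MB, Day 12: 264 − 2.17 = 261.8 h.

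Using Table 4's nominal end-of-infusion sample time (2.1333 h) instead gives 69.87 h for BA, which changes nothing.

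**Does the reading of the timing rule matter?** Administration could mean the oral dose (0 h) or the infusion (2 h). Both precede the end of the infusion, so the gaps above stand either way. The statement about t_max needs the oral-dose reading, which the 0 h column and criterion 13 support.

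**Contacts available.** After infusion start and before 72 h, Table 4 has blood samples at 2.1333, 3, 4, 6, 8, 10, 12, 24, 36 and 48 h. That is 10 contacts, none with a scheduled vital sign, ECG or site check.

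**Would a 3 h set fit?** From infusion end to 3 h is 50 min. Five minutes supine plus about 3 min for three readings is 8 min, leaving 42. With an ECG first: 10 min rest + about 1 min + 3 min = 14 min, leaving 36. Done just before 3 h, both fall inside ±15 min, and the PK draw can keep its ±10 min window (Section 8.5).

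**Staff time (assumed durations).** Two site checks at 1 to 2 min each take 2 to 4 min.
- Without ECG: 8 + (2 to 4) = 10 to 12 min per infusion.
- With ECG: 14 + (2 to 4) = 16 to 18 min per infusion.

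**Infusions affected.** There are 16 planned Period 2 infusions, plus up to 6 in the MB cohort if it is not yet dosed, which the documents do not say. Each BA replacement takes both periods, so it adds 2, less the Period 2 infusion of the participant replaced: net 1. Before replacements the total is 16 to 22.
- Without ECG: 16 × 10 = 160 min to 22 × 12 = 264 min (2.7 to 4.4 h).
- With ECG: 16 × 16 = 256 min to 22 × 18 = 396 min (4.3 to 6.6 h).

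**The case against.** The strongest reply is that the existing system has already worked. Period 1 pain was detected, attributed to a cause and followed by a halt. Trained staff give the infusion, participants stay in the unit, and AEs are sought at each contact (Section 8.3.1). Appendix 3 names infusion site reaction as a diagnosis and provides a dedicated eCRF for reactions during or within 24 h of administration. Symptom-directed examination is allowed, and Appendix 1 keeps explicit halting rules. Version 3 lowers the hazard by bringing potassium below 30 mmol/L. The IV dose is a 100 µg tracer, safety is not a primary objective, and Section 3 sets no timing for the safety endpoints.

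Most of this stands, and it limits the point. A reader might infer that infusion pain could go undetected, or that volunteers are left unobserved after the infusion. The documents do not support that: local reactions have a route to detection and recording. A reader might also infer that everyone still to be infused is being re-exposed. That is true only of BA participants continuing from Period 1 to Period 2; MB participants and BA replacements have had no earlier infusion in this study. Nor do vital signs or ECG measure pain, so the pain history supports the site check more directly than the vital-sign set.

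What the reply does not supply is an endpoint value. AE enquiry records what is reported or noticed; it does not produce a blood pressure, heart rate or ECG near the infusion or t_max. It also leaves the ±15-minute windows without a Day 1 time point.

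**Conclusion.** The gap is real and worth closing because closing it is cheap. As written, the plan schedules no vital sign, ECG or dedicated site check for 69.8 h after infusion end in the BA cohort and for 165.8 to 261.8 h in the MB cohort. The vital-sign and ECG endpoints therefore have no scheduled value near the infusion or the oral t_max.

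This rests on three things: the Section 8.9.2 default, since the tables give no post-dose time on Day 1; the absence of any overriding footnote in Tables 1 to 4; and the blank cells in those tables being truly blank. Unscheduled measurements prompted by symptoms remain possible and are not counted.

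It does not follow that the trial is unsafe or that AE capture is deficient. The missing ECG alone is a minor matter: either scheduling one or removing the unused window would resolve it.

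**What to change.** For every infusion still to be given, amend Tables 3 and 4, and Tables 1 and 2 if MB dosing is not complete:
- Add one triplicate vital-sign set at the existing 3 h contact, before the PK draw. This gives the Section 8.2.2 window a Day 1 time point.
- Add a brief infusion-site inspection at the end-of-infusion and 3 h contacts. Ask the non-directive AE question first and record the inspection separately, so that AE ascertainment stays the same across periods. Do not present it as a Period 1 versus Period 2 comparison, because Period 1 had no such check.
- Treat the ECG as optional. If one is added, take it at 3 h before the vital signs, as Section 8.2.3 requires. If not, delete the unused post-dose ECG window as an editorial correction.

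The cost is the assumed 10 to 12 minutes per infusion (16 to 18 with an ECG) worked out above, with no added visit or blood draw. The schedule and eCRF need updating, and IRB/EC and regulatory approval is needed if the change counts as substantial (Appendix 1, Section 2.3.1).
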